6.11.5. Vital Signs and Other Physical Findings

Vital sign data including blood pressure (BP), pulse rate (PR), temperature (T), respiratory rate (RR), height and weight will be listed and summarized for all patients on therapy. Patients with abnormal vital signs will be listed and summarized.

6.11.6. Electrocardiograms

For each patient, 12-lead ECGs will be obtained according to the Study Schedule (Protocol Attachment 1). All ECG's will be analyzed for safety and categorical analysis will be provided including:

1. Number and percentage of individuals with abnormal ECG findings.
2. Number and percentage of individuals with AEs that could be associated with prolongation of cardiac repolarization or proarrhythmia, e.g., palpitations, dizziness, syncope, cardiac arrhythmias and sudden death.

Categorical analysis of the following ECG parameter will be performed at day 1 and day 15 of each cycle and the short term follow up visit at the time points outlined in the protocol and changes will be compared to baseline (i.e. Cycle 1, Day 1 pre-dose). The analysis will include the number and percentage of individuals with:

1. Absolute QT/QTc values > 450 ms, > 480 ms, and > 500 ms; as well as the number and percentage of individuals with change from baseline > 30 ms and > 60 ms.
2. PR changes from baseline $\geq 50\%$ if baseline value is < 200 ms and $\geq 25\%$ of baseline value is ≥ 200 ms.
3. QRS changes from baseline $\geq 50\%$ if baseline value is < 110 ms and $\geq 25\%$ of baseline value is ≥ 110 ms.

6.11.7. Transfusion Data

Transfusion data will be listed for all patients on therapy by cohort.

6.11.8. X-Ray Data

Chest x-ray data will be listed for all patients on therapy by cohort.

6.12. Efficacy Analyses

As a coprimary objective for Part B, this study will evaluate preliminary antitumor activity observed with ramucirumab in combination with LY2875358 in the tumor-specific expansion cohorts.

Overall Response Rate (ORR): ORR is defined as the proportion of patients who exhibit a confirmed CR or PR relative to baseline as defined by RECIST 1.1 (Eisenhauer et al. 2009).

ORR is computed as the number of responders divided by the total number of treated patients. A responder is defined as any patient who exhibits a confirmed CR or PR relative to baseline

assessment, done on or up to 7 days prior to Cycle 1 Day 1. Patients with response that is deemed not evaluable will be considered non-responders and will be included in the denominator for the purpose of calculating ORR. ORR will be assessed within each cohort, ORR with 95% CIs will be estimated using the Clopper-Pearson method.

Progression-Free Survival (PFS): The PFS time is measured from the date of receiving the first dose of study drug to the date of first objective progression as assessed by the investigator or the date of death due to any cause, whichever is earlier. Table 6.2 provides additional details. The censoring is taken in the following order:

- If a patient does not have a complete baseline disease assessment, then the PFS time will be censored at the enrollment date, regardless of whether or not objectively determined disease progression or death has been observed for the patient; otherwise,
- If a patient is not known to have died or have objective progression as of the data inclusion cutoff date for the analysis, the PFS time will be censored at the last evaluable objective progression-free disease assessment date.

If a patient has a missed visit prior to an event (progression or death), then the PFS time will be censored at the last evaluable assessment prior to the event.

Table 6.2. Definition of PFS

Situation	Outcome	Date of Progression or Censoring
Death before first objective PD assessment	Progressed	Date of death
Objective PD	Progressed	Date of first radiologic assessment showing progressive disease
No evaluable baseline tumor assessments	Censored	Enrollment date
No progression	Censored	Date of last radiologic assessment of measured lesions showing no progression
New systemic anticancer treatment started	Censored	Date of last radiologic assessment of measured lesions showing no progression prior to the commencement of new systemic anticancer treatment
Death or progression after more than one missed visit (after 3 months since last assessment)	Censored	Date of last radiologic assessment of measured lesions showing no progression prior to the missed visit

The date of first documented objective disease progression must be recorded on the CRF even if it occurs after the patient has started a new therapy.

Disease Control Rate (DCR): The proportion of patients in the analysis population who exhibit an SD or confirmed CR or PR relative to baseline during the study. Response is defined by RECIST 1.1 (Eisenhauer et al. 2009).

Change in Tumor Size (CTS): The change in tumor size from baseline to the measurement with the smallest tumor size during the study period. Change in tumor size will be assessed in each patient using radiographic imaging. The tumor size of target lesions will be determined as defined by RECIST 1.1 (Eisenhauer et al. 2009).

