### **10.3. Efficacy Evaluations**

A secondary objective of the study is to document any antitumor activity. Refer to [Attachment 1](#) for details regarding the timing of specific efficacy measures. Efficacy measures include:

- ORR: The proportion of patients who exhibit a confirmed complete response (CR) or PR relative to baseline as defined by RECIST 1.1 (Eisenhauer et al. 2009)
- DCR: The proportion of patients in the analysis population who exhibit a SD or confirmed CR or PR relative to baseline during the study
- PFS: The time from the date of study enrollment to the date of first observation of objective progression or death from any cause
- Change in tumor size: The change in tumor size from baseline measurement to the measurement with the smallest tumor size during the study.

Each patient will be assessed by one or more of the following radiologic tests for tumor measurement:

- CT scan
- MRI
- Chest x-ray.

Each patient's full extent of disease will also be assessed with:

- Tumor measurement by RECIST 1.1 (Eisenhauer et al. 2009)
- Evaluation of tumor markers, if indicated
- Evaluation of ECOG performance status (refer to [Attachment 6](#)).

Consistent with RECIST, all patients may undergo alternative imaging studies consistent with institutional guidelines to assess tumor response. This may include, but is not limited to, FDG-PET, dynamic contrasted-enhanced MRI, or other modalities.

To confirm objective responses, all lesions should be radiologically assessed, and the same radiologic method used for the initial response determination should be repeated at least 4 weeks following the initial observation of an objective response, using the sample method that was used at baseline. If a patient is discontinued from the study, repeat radiology assessments may be omitted if clear clinical signs of progressive disease are present.

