## Screening/Baseline Assessments

Relative Day Prior to Day 1 of Cycle 1	≤28	≤14	≤7	Comments
Informed Consent	X			Informed consent MUST be signed before performing any protocol procedure
Radiological Tumor Assessment (including head-contrasted CT or brain MRI)	X			These scans can be performed locally and may be from prior to consent if taken within 28 days of Day 1, Cycle 1. PET/CT allowed if CT portion is of diagnostic quality
Chest X-Ray	X			May be omitted in patients having a chest CT for their radiological tumor assessment
Functional Tumor Imaging	X			FDG-PET mandatory in Part B1 (gastric). Further functional tumor imaging (including but not limited to DCE-MRI, FLT-PET) is permitted in all patients if appropriate for the respective tumor type at the discretion of the investigator and considered institutional standard of care or is part of an appropriate imaging study open at the site.
Hepatitis B and C Screening	X			Screening is required (see Attachment 2 ); may be from prior to consent if done within 6 months of Day 1, Cycle 1; Hepatitis B surface antigen and hepatitis C (antibodies or RNA according to local standard)
“Post-Progression Tumor Sample” (baseline)	X			Mandatory (see Section 10.2.1 ); may be from prior to consent if taken within 8 weeks of Day 1, Cycle 1. If this is not available, patient must undergo a tumor biopsy pre-study treatment
Archival Tumor Sample	X			Optional (see Section 10.2.2 )
Medical History		X		Including alcohol/tobacco use/other relevant habits
Physical Examination		X		Including height and body weight
Vital Signs		X		Temperature, blood pressure (seated), heart rate, and respiration rate
Performance Status		X		Per ECOG scale (see Attachment 6 )
CTCAE Version 4.03 Grading (Preexisting Conditions)		X		To be reported only after study eligibility is confirmed. Refer to Section 10.1.2 for reporting expectations.
Concomitant Medications		X		See Section 9.5
Local 12-Lead Electrocardiogram		X		Single ECG
Hematology		X		See Attachment 2
Serum Chemistry including calculated creatinine clearance		X		See Attachment 2
Coagulation		X		See Attachment 2
Urinalysis		X		See Attachment 2
Immunogenicity		X		
Sampling for Exploratory Blood Biomarkers		X		See Section 10.2.2

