**Specifications by Methods of Measurement**

All measurements should be recorded in metric notation, using a ruler or calipers if clinically assessed. All baseline evaluations should be performed as closely as possible to the beginning of treatment and never more than 4 weeks before the beginning of the treatment.

The same method of assessment and the same technique should be used to characterize each identified and reported lesion at baseline and during follow-up. Imaging-based evaluation is

should always be done rather than clinical examination unless the lesion(s) being followed cannot be imaged but are assessed by clinical exam.

An adequate volume of a suitable contrast agent should be given so that the metastases are demonstrated to best effect and a consistent method is used on subsequent examinations for any given patient. If prior to enrollment it is known a patient is not able to undergo CT scans with IV contrast due to allergy or renal insufficiency, the decision as to whether a non-contrast CT or MRI (with or without IV contrast) should be used to evaluate the patient at baseline and follow-up should be guided by the tumour type under investigation and the anatomic location of the disease.

*Clinical Lesions:* Clinical lesions will only be considered measurable when they are superficial and  $\geq 10$  mm diameter as assessed using calipers (for example, skin nodules). For the case of skin lesions, documentation by color photography, including a ruler to estimate the size of the lesion is recommended. When lesions can be evaluated by both clinical exam and imaging, imaging evaluation should be undertaken since it is more objective and may be reviewed at the end of the study.

*Chest X-ray:* Chest CT is preferred over chest X-ray when progression is an important endpoint. Lesions on chest X-ray may be considered measurable if they are clearly defined and surrounded by aerated lung.

*CT and MRI:* CT scan is the best currently available and reproducible method to measure lesions selected for response assessment. Measurability of lesions on CT scan is based on the assumption that CT slice thickness is  $\leq 5$  mm. When CT scan have slice thickness  $>5$  mm, the minimum size for a measurable lesion should be twice the slice thickness. MRI is also acceptable in certain situations (for example, for body scans). If there is concern about radiation exposure at CT, MRI may be used instead of CT in selected instances.

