### Evaluation of Best Overall Response

The best overall response is the best response recorded from the start of the study treatment until the earliest of objective progression or start of new anticancer therapy, taking into account any requirement for confirmation. The patient's best overall response assignment will depend on the findings of both target and nontarget disease and will also take into consideration the appearance of new lesions. The Best Overall Response will be calculated via an algorithm using the assessment responses provided by the investigator over the course of the trial.

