### Frequency of Tumor Re-Evaluation

A baseline tumor evaluation must be performed within 4 weeks before patient begins study treatment. Frequency of tumor re-evaluation while on and adapted to treatment should be protocol-specific and adapted to the type and schedule of treatment. In the context of Phase 2 studies where the beneficial effect therapy is not known, follow-up every 6-8 weeks is reasonable. Normally, all target and non-target sites are evaluated at each assessment using the same method. However, bone scans may need to be repeated only when CR is identified in target disease or when progression in bone is suspected.

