In case of significant clinical activity in any of the tumor-specific expansion cohorts, further patients may be added to enroll up to approximately 45 patients per cohort to further characterize the safety and explore clinical activity of LY2875358 in combination with a fixed regimen of ramucirumab treatment, if deemed appropriate after discussion and mutual agreement between the investigators and the sponsor. A sample size of 45 would give us a weighted average power of 83% based on 2-sided type I error rate of 5% to detect the significant dependence between biomarker status and clinical response as above. The criterion of significant clinical activity may vary based on tumor-specific response rates or landmark disease control. Table JTBF 5.2 summarizes the parameters of Simon's optimal two-stage design for each cohort. The uninteresting RR of Gastric/GEJ, HCC, RCC are referenced from previous trials JVBD, JVBPQ and JVBP (Fuchs et al. 2013). The uninteresting RR of NSCLC is based on the average RR of squamous and nonsquamous groups in the second-line docetaxel arm (Scagliotti et al. 2011). Alternatively, disease control may be considered in order to proceed with enrollment up to 45 patients per cohort if deemed appropriate. Table JTBF 5.3 summarizes landmark disease control and landmark disease control considered of interest to enroll up 45 patients per cohort. Such decisions will be documented in writing, and a written notification will be sent to the IRB prior to enrollment of further patients.

Table JTBF.5.2. Simon's Optimal Two-stage Design Parameters for Each Cohort

Tumor Type	Uninteresting RR	Favorable RR	1-sided Type I Error Rate	Power	n ₁	n	r ₁	r
Gastric/GEJ	3%	10%	0.15	0.7	14	45	1	3
HCC	10%	22%	0.1	0.75	14	42	1	7
RCC	5%	12%	0.15	0.7	13	45	1	4
NSCLC	8.5%	22%	0.1	0.8	14	41	2	6

Abbreviations: GEJ=gastroesophageal junction; HCC=hepatocellular carcinoma; n₁=number of patients enrolled in the first stage; n=total number of patients enrolled; NSCLC=non-small cell lung cancer; r₁=number of responses required to proceed to the second stage; r=total number of responses required for further investigation of the drug; RCC=renal cell carcinoma; RR=response rate.

Table JTBF.5.3. Previously Observed Antitumor activities of Ramucirumab Monotherapy on Gastric or GEJ adenocarcinoma, Hepatocellular carcinoma, and Renal cell cancer

Tumor Type	Study	n	mPFS	mOS	ORR	DCR	Landmark	Secondary CSF
Gastric/GEJ	JVBD	355	2.1mos	5.2 mos	3%	49%	12-wks PFS 40%	60%

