6.3. Handling of Dropouts or Missing Data

Missing data will not be imputed.

In Part B, patients with response that is deemed non-evaluable will be included in the denominator for the purpose of calculating ORR. Non-evaluable patients are patients who do not have a measurable disease at baseline or patients who do not have any post-baseline assessment performed.

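### SAP 6.12 counts Part B responses only against a baseline scan from the last 7 days before dosing, but the protocol accepts scans up to 28 days old, so the co-primary ORR can come out two ways

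*SAP*

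**What the plan says.** SAP 6.12 (Efficacy Analyses) defines ORR twice. The opening definition is confirmed complete or partial response by RECIST 1.1, with no limit on the age of the baseline scan. The next paragraph defines a responder relative to a baseline "assessment, done on or up to 7 days prior to Cycle 1 Day 1". ORR is responders divided by all treated patients, and patients who are not evaluable count as non-responders.

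The protocol sets a different window:

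- Attachment 1, Screening/Baseline Assessments, lists the radiological tumor assessment under 28 days. Scans "may be from prior to consent if taken within 28 days of Day 1, Cycle 1".
- Attachment 8, Specifications by Methods of Measurement, says baseline evaluations are to be "never more than 4 weeks before the beginning of the treatment".
- Attachment 8, Frequency of Tumor Re-Evaluation: "A baseline tumor evaluation must be performed within 4 weeks before patient begins study treatment".
- Section 10.3 defines ORR as confirmed response "relative to baseline as defined by RECIST 1.1", with no 7-day term.

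Two further passages bear on classification. SAP 6.3 says: "Non-evaluable patients are patients who do not have a measurable disease at baseline or patients who do not have any post-baseline assessment performed". Attachment 8, Evaluation of Best Overall Response, says best response is "calculated via an algorithm using the assessment responses provided by the investigator over the course of the trial".

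**The concern.** A site that follows the protocol exactly can produce baseline scans that the SAP's responder definition does not recognise. After baseline, Attachment 1 schedules tumor imaging every 6 weeks from the start of treatment, so nothing obliges a site to rescan in the last week before dosing.

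The co-primary endpoint is then not uniquely defined: two analysts working from the same SAP and the same data could report different ORRs. The study is open-label, so a choice between readings made at analysis would be made with the responses already known, which a pre-specified definition is meant to prevent. Cohorts are small (about 15), and the sample-size argument in protocol 8.1.1 and SAP 5.2 turns on seeing at least 1 responder, so single patients matter.

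**Working it through.** **1. The two readings side by side.** Take a treated patient with measurable disease, a baseline scan 20 days before Cycle 1 Day 1, and a confirmed partial response.

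| Text applied | Classification |
|---|---|
| Protocol Attachments 1 and 8 | Baseline scan is compliant |
| SAP 6.12, responder sentence taken literally | Not a responder; kept in the denominator |
| SAP 6.12, opening ORR sentence; protocol 10.3 | Responder |
| SAP 6.3 | Evaluable: measurable disease at baseline and a post-baseline assessment are both present |
| Attachment 8, best overall response | Responder: scan timing is not tested |

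No passage settles the conflict. The denominator is the same under both readings, so the literal one can only lower ORR.

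**2. Effect of one patient.** With n = 15, one response is 1/15 = 6.7 percentage points. Clopper-Pearson 95% limits (the SAP's method) are the 0.025 quantile of Beta(x, n−x+1) and the 0.975 quantile of Beta(x+1, n−x):

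| Responders of 15 | ORR | 95% CI |
|---|---|---|
| 2 | 13.3% | 1.7% to 40.5% |
| 1 | 6.7% | 0.2% to 31.9% |
| 0 | 0% | 0% to 21.8% |

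**3. The plan's own figures.** P(at least 1 of 15) = 1 − (1 − p)^15. At p = 0.10 this is 79.4% (stated 79%); at p = 0.03 it is 36.7% (stated 36.7%). Both reproduce, and both assume that every response counts.

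**4. Cohort-level bound under the literal reading.** Let f be the share of patients whose baseline scan is older than 7 days. The documents do not give f, so a range is shown, with f assumed unrelated to response. If every response on an older scan is discarded, the countable response rate is RR × (1 − f).

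The stage 1 inputs come from the Simon table (protocol Table JTBF.1, SAP Table JTBF.5.2): gastric n1 = 14, r1 = 1, RR 10%; NSCLC n1 = 14, r1 = 2, RR 22%. The footnote describes r1 as the number of responses needed to proceed, so it is read as at least r1. That reading returns the tabulated power overall: 70.1% for gastric (stated 0.7) and 80.6% for NSCLC (stated 0.8). With q = RR × (1 − f):

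- gastric: 1 − (1 − q)^14
- NSCLC: 1 − (1 − q)^14 − 14q(1 − q)^13

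| f | At least 1 of 15, RR 10% | At least 1 of 15, RR 3% | Gastric, at least 1 of 14 | NSCLC, at least 2 of 14 |
|---|---|---|---|---|
| 0 | 79.4% | 36.7% | 77.1% | 84.7% |
| 10% | 75.7% | 33.7% | 73.3% | 79.7% |
| 25% | 68.9% | 28.9% | 66.4% | 69.8% |
| 50% | 53.7% | 20.3% | 51.2% | 46.6% |
| 75% | 31.6% | 10.7% | 29.8% | 17.8% |

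These figures show what the literal rule would do for a given f. They are not a demonstrated loss of power.

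**The case against.** The strongest reply is that the 7-day clause is a drafting slip that no sensible analyst would apply. In the screening schedule the 7-day column holds only the serum pregnancy test. The opening ORR sentence of SAP 6.12, protocol 10.3, both Attachment 8 windows, SAP 6.3 and the best-response rule all point towards counting the response. SAP Table JTBF.6.1 also takes baseline as the last value reported before the first dose, with no day limit, and partial response is measured against baseline diameters. In addition, the analyses are descriptive, f is unknown, and expansion beyond about 15 patients happens only "if deemed appropriate after discussion and mutual agreement between the investigators and the sponsor", with disease control as an alternative ground. A lost response therefore need not close a cohort.

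Much of this stands. The weight of the text favours counting the response, and if every scan fell within 7 days the two ORRs would coincide. The cohort-level table is illustrative for the same reason.

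It does not remove the conflict. The Table JTBF.6.1 rule is worded for change-from-baseline analyses and does not clearly override a specific responder definition. The other passages contradict the clause; none withdraws it. To reach the sensible answer an analyst must disregard part of the written definition of a co-primary endpoint.

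**Conclusion.** The point holds and should be fixed. The SAP's responder definition conflicts with the protocol's baseline window, and nothing in either document reconciles them. What is certain is the direction (the literal reading can only lower ORR) and the size per patient (6.7 points in a cohort of 15). The size across a cohort rests on two assumptions: the unknown share of scans older than 7 days, and strict application of the clause. ORR is the co-primary result and one input to the expansion decision, but not a binding rule for it, so the consequence is an ambiguous endpoint rather than a proven loss of power.

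**What to change.** In SAP 6.12, replace the 7-day phrase with: *the last evaluable tumor assessment within 28 days before the first dose*. This matches protocol Attachments 1 and 8. Add one sentence stating that the same tumor baseline applies to disease control rate, change in tumor size and PFS. It would also help to say how a response is classified when the only baseline scan falls outside 28 days; that would be a protocol deviation and is a minor residual gap.

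The cost is one phrase and one clarifying sentence in the SAP, plus the optional line on out-of-window scans. No new data and no protocol amendment are needed. With the 28-day window, the 79% and 36.7% in the sample-size section stand unchanged.

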In case of significant clinical activity in any of the tumor-specific expansion cohorts, further patients may be added to enroll up to approximately 45 patients per cohort to further characterize the safety and explore preliminary clinical activity of LY2875358 in combination with a fixed regimen of ramucirumab treatment, if deemed appropriate after discussion and mutual agreement between the investigators and the sponsor. A sample size of 45 would give us a weighted average power of 83% based on 2-sided type 1 error rate of 5% to detect the significant dependence between biomarker status and clinical response as above. The criterion of significant clinical activity may vary based on tumor-specific response rates or landmark disease control. [Table JTBF.1](#) summarizes the parameters of Simon's optimal two-stage design for each cohort. The uninteresting RR of Gastric/GEJ, HCC, RCC are referenced from previous trials JVBD, JVBD and JVBP. The uninteresting RR of NSCLC is based on the RR in the second-line docetaxel arm (Scagliotti et al. 2011). Alternatively, disease control may be considered in order to proceed with enrollment up to 45 patients per cohort if deemed appropriate. [Table JTBF.2](#) summarizes landmark disease control and landmark disease control considered of interest to enroll up 45 patients per cohort. Such decisions will be documented in writing following discussions between the investigators and the sponsor, and a written notification will be sent to the IRB prior to enrollment of further patients.

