**Table JTBF.1. Simon's Optimal Two-stage Design Parameters for Each Cohort**

Tumor Type	Uninteresting RR	Favorable RR	1-sided type 1 error rate	Power	$n_1$	n	$r_1$	r
Gastric/GEJ	3%	10%	0.15	0.7	14	45	1	3
HCC	10%	22%	0.1	0.75	14	42	2	7
RCC	5%	12%	0.15	0.7	13	45	1	4
NSCLC	8.5%	22%	0.1	0.8	14	41	2	6

Abbreviations: GEJ = gastroesophageal junction; HCC = hepatocellular carcinoma;  $n_1$  = number of patients enrolled in the first stage; n = total number of patients enrolled; NSCLC = non-small cell lung cancer;  $r_1$  = number of responses required to proceed to the second stage; r = total number of responses required for further investigation of the drug; RCC = renal cell carcinoma; RR = response rate.

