5.2. Determination of Sample Size

To determine a recommended schedule and dose range of LY2875358 in combination with ramucirumab that may be safely administered to patients with advanced and/or metastatic cancer, an adequate patient sample size is required. A sufficient sample size will allow for an accurate evaluation of the relationship between exposure and toxicity, as well as an evaluation of the relationship between exposure and pharmacological effects using descriptive statistics and appropriate modeling techniques, if data warrant. This sample size is estimated to be a total of approximately 70 patients (6-12 [Part A] + 60 [Part B]).

For Part A, following a 3+3 dose escalation scheme, the sample size calculation assumes that cohorts will include 3 to 6 patients. If 2 cohorts for the intended 2 dose levels for LY2875358 (i.e., 750 and 2000 mg) are needed to determine a recommended dose range for LY2875358 in combination with ramucirumab, then approximately 6-12 patients will be enrolled in Part A. To ensure accurate evaluation of safety, tolerability, or PK/PD biomarkers, additional patients may be enrolled during Part A if deemed appropriate based on agreement between the investigators and the sponsor.

For Part B, the sample size of approximately 15 patients per expansion cohort was selected to allow adequate confirmation of safety and tolerability of LY2875358 in combination with ramucirumab and to identify evidence of preliminary clinical activity worthy of further investigation in Phase 2, analogous to the first stage of a Simon 2-stage design. If the true clinical RR according to RECIST for the combination of ramucirumab and LY2875358 in 1 of the tumor types selected is 10%, then there is a 79% chance of observing at least 1 patient with a clinical response, which might warrant further study of the regimen. On the other hand, if the true RR is close to the RR of ramucirumab monotherapy (for example, 3% in the REGARD trial, Table JTBF.5.2), then there is a 36.7% chance of incorrectly concluding that the regimen merits further study. Table JTBF.5.1 demonstrates chance of observing at least 1 patient with clinical response for the combination of ramucirumab and LY2875358. For instance, if the true clinical RR is 10% across all four expansion cohorts in part B, there is 49.3% probability of observing

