6.16. Interim Analyses and Data Monitoring

An interim analysis will be performed after completion of Part A. Data will be reviewed on a cohort-by-cohort basis during the study until the MTD is determined. The purpose of these cohort-by-cohort reviews is to evaluate the safety data at each dose level and to determine if a DLT has been observed that would suggest MTD has been met or exceeded.

For Part B, both safety and efficacy data will be assessed. Interim analyses will be conducted after approximately 15 patients have completed 3 cycles in Parts B1,B2 and B4 (gastric, hepatocellular cancers and non-small cell lung cancer) and 6 cycles in Part B3 (renal cell cancer).

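### In a cohort expanded on a good first look, the planned pooled ORR still counts the patients who triggered expansion, so given expansion the co-primary estimate reads high

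*SAP*

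**What the plan says.** ORR in the tumor-specific cohorts is the co-primary objective for Part B (Protocol 6.1, SAP 4.1). The first group of about 15 patients is described as "analogous to the first stage of a Simon 2-stage design" (SAP 5.2). If activity is significant, "further patients may be added to enroll up to approximately 45 patients per cohort" (Protocol 8.1.1). The criterion may be response, using the cut-offs in Protocol Table JTBF.1 and SAP Table JTBF.5.2, where r1 is the "number of responses required to proceed to the second stage". It may also be a landmark: "Alternatively, disease control may be considered in order to proceed with enrollment up to 45 patients per cohort if deemed appropriate" (SAP 5.2). The decision follows a look at the data: "Interim analyses will be conducted after approximately 15 patients have completed 3 cycles in Parts B1,B2 and B4", with 6 cycles for the renal cohort (SAP 6.16).

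For the analysis, SAP 6.12 says "ORR is computed as the number of responders divided by the total number of treated patients" and adds "ORR will be assessed within each cohort, ORR with 95% CIs will be estimated using the Clopper-Pearson method". It gives no estimate by stage, no estimate that allows for the expansion decision, and no separate result for the added patients. Pooling is not stated in so many words; it follows from the denominator.

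**The concern.** A cohort reaches 41 to 45 patients only if its first patients did well enough. Among cohorts that get there, the first-stage response count is therefore higher on average than the true rate would give. The added patients carry no such selection. Combining the two dilutes the excess but does not remove it.

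The ORR in an expanded cohort is the figure most likely to be carried forward. The excess is largest when the combination adds nothing over the uninteresting rate, which is when a flattering estimate does most harm.

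**Working it through.** **Inputs.** Uninteresting rate p0, favorable rate p1, first-stage size n1, total n, r1 and r come from Protocol Table JTBF.1; the gastric row reads "Gastric/GEJ 3% 10% 0.15 0.7 14 45 1 3". SAP Table JTBF.5.2 is identical except that HCC has r1 = 1 instead of 2.

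**Step 1: reproduce the plan's figures.** At least one response in 15: 1 − 0.90^15 = 79.4% and 1 − 0.97^15 = 36.7%, as stated. For the tables, continue if X1 ≥ r1 and succeed if the total is ≥ r. This gives one-sided error/power of 0.110/0.701 (gastric), 0.098/0.761 (HCC, r1 = 2), 0.149/0.701 (RCC) and 0.097/0.806 (NSCLC), all within the stated limits. HCC with r1 = 1 gives 0.117/0.834 against the stated 0.10/0.75, so only r1 = 2 fits the stated error rate.

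**Step 2: pooled ORR given expansion on r1.** With true rate p,

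E[pooled ORR | X1 ≥ r1] = {E[X1 | X1 ≥ r1] + (n − n1)p} / n.

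- Gastric, p = 0.03: E[X1 | X1 ≥ 1] = 14 × 0.03 / (1 − 0.97^14) = 0.42 / 0.3472 = 1.210. Added patients contribute 31 × 0.03 = 0.93. Result: 2.140 / 45 = 4.8%.
- NSCLC, p = 0.085: E[X1 | X1 ≥ 2] = 1.19 × (1 − 0.915^13) / 0.3367 = 2.421. Added patients contribute 27 × 0.085 = 2.295. Result: 4.716 / 41 = 11.5%.

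| Cohort | Chance of expansion at p0 | p0 reads | Bias (points) | p1 reads | Bias (points) |
|---|---|---|---|---|---|
| Gastric | 34.7% | 3% → 4.8% | +1.8 | 10% → 10.9% | +0.9 |
| HCC, r1 = 2 | 41.5% | 10% → 12.65% | +2.65 | 22% → 23.0% | +1.0 |
| HCC, r1 = 1 | 77.1% | 10% → 11.0% | +1.0 | 22% → 22.2% | +0.2 |
| RCC | 48.7% | 5% → 6.5% | +1.5 | 12% → 12.8% | +0.8 |
| NSCLC | 33.7% | 8.5% → 11.5% | +3.0 | 22% → 23.0% | +1.0 |

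The look is planned at about 15 patients, not 13 or 14. With 15 then 45 patients and the same r1 (HCC at 2), the bias is +1.4 to +2.6 points at p0 and +0.7 to +0.9 at p1.

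**Step 3: the disease-control route.** The documents do not link response to landmark status. Assume that every responder is progression-free at the landmark, that true landmark PFS equals the previously observed value (40% gastric, 50% others), and that a cohort goes from 15 to 45 patients if at least 9 of 15 (gastric) or 12 of 15 (others) reach the landmark. The bias at p0 is then +0.6 (gastric), +2.1 (HCC), +1.1 (RCC) and +1.8 (NSCLC) points.

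**Step 4: the interval.** Exact enumeration given expansion on r1, at p0 and p1, gives two-sided Clopper-Pearson coverage of 94.7% to 98.5%. At p0 the lower limit exceeds the truth in 2.8% (gastric), 4.6% (HCC, r1 = 2), 4.4% (RCC) and 5.3% (NSCLC) of expanded cohorts, against a nominal 2.5%.

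**Step 5: which correction fits.** Write n2 = n − n1 and s for total responders. The estimate that is unbiased given expansion (UMVCUE) is

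Σ C(n1, x) C(n2 − 1, s − x − 1) / Σ C(n1, x) C(n2, s − x), over x ≥ r1.

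Gastric at 3/45: (14 × 30 + 91 × 1) / (6510 + 2821 + 364) = 511 / 9695 = 5.3%, against the pooled 6.7%. The usual two-stage UMVUE, which replaces the numerator by Σ C(n1 − 1, x − 1) C(n2, s − x), gives (465 + 403 + 78) / 9695 = 9.8%.

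| At the tabled r | Pooled | UMVCUE | UMVUE |
|---|---|---|---|
| Gastric 3/45 | 6.7% | 5.3% | 9.8% |
| HCC 7/42 (r1 = 2) | 16.7% | 15.0% | 20.1% |
| RCC 4/45 | 8.9% | 7.7% | 11.7% |
| NSCLC 6/41 | 14.6% | 12.5% | 18.8% |

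**The case against.** The analyses are called descriptive (Protocol 12.1, SAP 6.1), and Protocol 12.6 says the study was not designed for a comparative efficacy assessment. No formal test is invalidated, and at the favorable rates a bias of about 1 point is small beside an interval such as 1.4% to 18.3% at 3/45. This stands and limits the consequence. But a descriptive co-primary estimate should still describe the true rate, and at the uninteresting rates the relative excess is 27% to 59% (HCC with r1 = 2).

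Expansion is discretionary and need not follow r1. This also stands: the table in step 2 shows what happens if r1 is applied, not what the documents guarantee. If response played no part in the decision, directly or through disease control, there would be no bias.

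Three stronger readings are tempting and are not supported:

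- **That the pooled ORR is biased upward overall.** Over stopped and expanded cohorts together it is biased downward, by 1.4 to 2.2 points at p0 with the protocol's cut-offs (gastric 3% reads 1.7%). The upward bias is conditional on expansion.
- **That Clopper-Pearson fails.** Two-sided coverage holds; the excess is confined to the lower limit.
- **That selection explains why the 95% lower limits at exactly r (1.4%, 7.0%, 2.5%, 5.6%) fall below the uninteresting rates.** That comes from setting a two-sided 95% interval beside designs with 10% or 15% one-sided error. It would occur in a single-stage trial too.

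**Conclusion.** The point holds for cohorts expanded on response or on a correlated measure. Given expansion on the tabled r1, the pooled ORR is too high by about 1.5 to 3.0 points at the uninteresting rates and 0.8 to 1.0 point at the favorable rates; for HCC under the SAP's r1 = 1 the figures are 1.0 and 0.2. These sizes assume that r1 is applied as tabled and that the first-look patients stay in the denominator, as the SAP wording implies. The disease-control figures rest on the further assumptions in step 3. The interval is adequate two-sided, with a modest one-sided excess (up to 5.3% against 2.5%). This is a reporting gap that is cheap to close, not a flaw that undermines the design.

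**What to change.** In SAP 6.12, for any cohort expanded beyond the first look:

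- Keep the pooled ORR, and report beside it the ORR and exact 95% interval in patients enrolled after the first look, whose data did not inform the decision. This estimate is free of the selection whichever trigger was used.
- Record which trigger, response or disease control, led to expansion.
- Where expansion followed r1, optionally add the UMVCUE. Do not use the UMVUE for this purpose: it targets stopped and expanded cohorts together and raises the estimate in an expanded one.
- Reconcile the HCC r1 (2 in the protocol, 1 in the SAP), since the UMVCUE depends on it.

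The cost is a few lines of SAP text and one table row, with no new data. The downside is precision: the added-patient result rests on about 27 to 32 patients (41 − 14 to 45 − 13). For example, if one of three gastric responders came from the first look, the added patients give 2/31 = 6.5% with a Clopper-Pearson interval of 0.8% to 21.4%, against 1.4% to 18.3% for 3/45.
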